
OBJECTIVE/REASON:

The aim of the project is to develop the "Let's Move" mobile software program based on the Transtheoretic Model (TTM) and to test the effect of the developed program on changing the sedentary life behaviors of its students.

Project Goals

- The developed TTM based 'Let's Move' mobile software program will be effective in changing the sedentary behaviors of students.
- The number of steps of the experimental group will increase.
- The physical activity Metabolic Equivalent (MET) scores of the experimental group will increase.
- The ratio of inactive and minimally active students in the experimental group will decrease, and the ratio of students in the very active category will increase.
- The percentage of students in the experimental group TTM behavior change preparation and action phase will increase.
- The cognitive change processes scores of the experimental group will increase.
- The behavioral change processes scores of the experimental group will increase.
- The self-efficacy score of the experimental group will increase.
- Decision-making utility perception score of the experimental group will decrease.
- The decision-making harm perception score of the experimental group will increase.
- The proportion of those with normal Body Mass Index (18.5-24.99) in the experimental group will increase.
- The International Physical Activity Questionnaire (IPAQ) scores of the experimental group will increase.
- Total body muscle ratio of the experimental group will increase.
- The body fat ratio of the experimental group will decrease.

SUBJECT and SCOPE

Sedentary lifestyle is an important behavioral problem that threatens health and is reported to be common among young people (WHO, 2020; Ceylan, 2020; Kim et al., 2020; Han et al., 2017; Prochaska et al., 2017). University years include adolescence and young adulthood. In order to reach the healthy adults of the future, it is very important to spend these periods active, to gain healthy lifestyle behaviors and to make them permanent. Adopting an inactive lifestyle of young people causes many non-communicable diseases (diabetes, hypertension, hyperlipidemia, etc.) in later ages (Kleis et al. 2022; Güler, 2022). For this reason, developing

an active lifestyle and changing an inactive lifestyle during the youth years are the most important components of reaching healthy societies.

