6.2.4. Transtheoretic Model Sedentary Life Decisional Balance Scale (SL-DBS) (Annex 5)

The decision-making scale consists of two sub-dimensions that measure the benefits and harms of making a behavior change decision. The sedentary life decision-making scale consists of 12 items containing the positive and negative aspects of sedentary life.

6.2.4.1. Decision-making utility sub-dimension; A high score on this sub-dimension indicates that they are aware of the benefits of behavior change and that they are more likely to change their behavior. The scale consists of 1, 3, 5, 7, 9, and 11 items, and the Cronbach Alpha reliability coefficient of the Turkish version is 0.87.

6.2.4.2. Decision making harm sub-dimension; A high score on this sub-dimension indicates that the harms of behavior change attract more attention and the probability of changing behavior is less. It consists of items 2, 4, 6, 8, 10, and 12 of the scale, and the Cronbach Alpha reliability coefficient of the Turkish version was stated as 0.73 (Tok, 2017).

6.2.5. International Physical Activity Questionnaire (IPAQ) (Annex 6);

The International Physical Activity Survey (IPAQ) was developed as a tool for international monitoring of physical activity and inactivity. It consists of seven questions to determine the average daily time spent sitting, walking, and moderate to vigorous activity over the past seven days. Between 1997 and 1998, an International Association Group developed four long and four short forms of IPAQ tools (phone call or self-administration, two alternate reference periods, "last 7 days" or "regular week" "remembered physical activity)" (IPAQ research Committee Guidelines for data processing and analysis of International Physical Activity Questionnaire (http://www.ipaq.ki.se, accessed 28.04.2021).

Scoring and Scoring the IPAQ Questionnaire

Short form (7 questions); provides information on time spent walking, moderate and vigorous activities, and time spent sitting. Calculation of the total score of the short form includes the sum of the duration (minutes) and frequency (days) of walking, moderate-intensity activity, and

vigorous activity. The energy required for activities is calculated with the MET-minute score. Standard MET values have been established for these activities.

Physical Activities	MET value	Weekly MET score calculation (min*day)
	(min.)	
Walk	3.3 MET	Walking MET-min/week = 3.3 x walking minutes x
		number of walking days

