Appendix 7. TTM Sedentary Life Decision Balance Scale (SL-DBS)						
Dec	ision Balance Scale					
This	s section examines the positive and negative aspects of					
sed	entary behaviors.		ıt	nt		
Rea	d the following statements carefully and consider the degree of		ortan	orta		nt
sign	ificance of these statements.	atter	mpc	imp	ant	ortai
In e	ach statement, think about how you feel now, not how you felt	t ma	at I	tely	orta	mpc
or v	vanted to feel in the past. Please circle the number that best	s no	ewh	lera	imp	hly i
des	cribes you.	Doe	Som	moc	Very	Hig
1.	Reducing my sitting time allows me to have a more positive outlook on life.	1	2	3	4	5
2.	If I reduce the amount of time I sit, I will feel tired during the day.	1	2	3	4	5
3.	Avoiding inactivity will be beneficial for my health.	1	2	3	4	5
4.	When I do something to avoid inactivity, I feel like I'm wasting my time. For example, taking a walk instead of sitting and studying.	1	2	3	4	5
5.	If I avoid inactivity, I feel more industrious.	1	2	3	4	5
6.	When I take a break to move while studying, my concentration breaks down.	1	2	3	4	5
7.	I feel proud of myself when people see my effort not to be too inactive and accept me as a role model.	1	2	3	4	5
8.	Spending sedentary time is very convenient and comfortable for me.	1	2	3	4	5
9.	Avoiding inactivity makes me an active person.	1	2	3	4	5
10	When I reduce the energy I spend by being inactive, I feel good.	1	2	3	4	5
11	avoiding inactivity; It helps to regenerate both my body and my brain.	1	2	3	4	5
12	It bothers me to move around where everyone is still. For example, getting up and moving while reading a book in the library or watching TV with friends.	\neg	2	3	4	5

Transtheoretic Model Sedentary Life Decision Balance Scale (SL-DBS) (Annex7)

The decision-making scale consists of two sub-dimensions that measure the benefits and harms of making a behavior change decision. The sedentary life decision-making scale consists of 12 items containing the positive and negative aspects of sedentary life.

- Sedentary life behavior change decision-making benefit perception subdimension; It consists of 1, 3, 5, 7, 9, and 11 items of the scale. The minimum score to be taken from these scales will be '6' and the maximum score will be '30'. A high score on this sub-dimension indicates that they are aware of the benefits of behavior change and that they are more likely to change their behavior.

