- Sedentary life behavior change decision making harm sub-dimension; It consists of the 2nd, 4th, 6th, 8th, 10th, and 12th items of the scale. The minimum score to be taken from these scales will be '6' and the maximum score will be '30'. A high score on this sub-dimension indicates that the harms of behavior change attract more attention and the probability of changing behavior is less.

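### The two decisional-balance goals (utility down, harm up) run opposite to the protocol's own scoring of the SL-DBS

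*Protocol*

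**What the plan says.** **Goals.** The Project Goals list 14 expectations. The ninth is "Decision-making utility perception score of the experimental group will decrease" and the tenth is "The decision-making harm perception score of the experimental group will increase".

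**Scoring.** Section 6.2.4.1 says of the utility subscale: "A high score on this sub-dimension indicates that they are aware of the benefits of behavior change and that they are more likely" to change. Section 6.2.4.2 says of the harm subscale that a high score indicates that "the harms of behavior change attract more attention and the probability of changing behavior is less". Appendix 7 repeats both statements, gives each subscale a range of 6 to 30, and names them "Sedentary life behavior change decision-making benefit perception subdimension" and "Sedentary life behavior change decision making harm sub-dimension".

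**A second description.** The introduction to the scale, in Section 6.2.4 and again in Appendix 7, speaks of "12 items containing the positive and negative aspects of sedentary life". The module aims in Section 7 also refer to sedentary life. All five stages aim to raise its perceived harm, or to keep it high. The preparation, action and maintenance stages aim to lower its perceived benefit as well.

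**Use.** Section 9 lists both subscale means as dependent variables, without direction. Section 10 compares the groups by t test or Mann-Whitney U at p<0.05 and does not state whether tests are one- or two-sided.

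**The concern.** A goal that names a score and a direction is a hypothesis about that score. Under the protocol's scoring, a falling utility score and a rising harm score both mean that students have become less likely to change. The trial would then be predicting that its programme worsens decisional balance while it improves stage of change, change processes and self-efficacy.

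If results are judged against the goals as written, a favourable shift on either subscale refutes its hypothesis and an unfavourable one confirms it. If the direction is instead corrected after the data are seen, the sign has been chosen post hoc, which is hard to defend for a listed outcome.

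**Working it through.** The sign conflict needs no arithmetic. It follows from setting the texts side by side.

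**1. Goal against scoring**

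| Subscale | Items | Goal | Meaning of a high score (6.2.4, Appendix 7) | Favourable direction |
|---|---|---|---|---|
| Utility | 1, 3, 5, 7, 9, 11 | Down | Change more likely | Up |
| Harm | 2, 4, 6, 8, 10, 12 | Up | Change less likely | Down |

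Each subscale has six items scored 1 to 5, so the range is 6×1 = 6 to 6×5 = 30, as Appendix 7 states. No section reverses an item or a subscale. Both goals have the opposite sign: 2 of 14.

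**2. Do the items support the scoring text?**

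- Utility: all six items state a gain from sitting less or avoiding inactivity (outlook, health, industriousness, pride, being active, renewal of body and brain).
- Harm: items 2, 4, 6 and 12 state a cost of moving or sitting less (tiredness, wasted time, broken concentration, discomfort in front of others).
- Item 8, "Spending sedentary time is very convenient and comfortable for me", is an advantage of sedentary life, yet it sits in the harm subscale. It fits a subscale of reasons against change and does not fit one of harms of sedentary life.
- Item 10 is unclear in the English text and is left out of the argument.

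A student helped by the programme would be expected to endorse the odd items more and the even items less, the reverse of both goals.

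**3. The protocol's own precedent.** The literature review reports a model-based WhatsApp study in adolescents. There, benefit perception rose and harm perception fell, together with progress through the stages, as the successful result.

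**4. Consequence for a test (illustration only).** Inputs from Section 4 (Sample): d = 0.5, α = 0.05, power 0.95, 88 per group, 97 with the 10% addition. The value 0.5 is the planning effect size, not an SL-DBS estimate. Sidedness is not stated.

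- The plan's own figure: an independent t test needs 87.3 per group one-sided, hence 88 and a total of 176, as stated. Two-sided it needs 104.9, hence 105. So 176 reproduces only as a one-sided calculation. 176 × 1.10 = 193.6, hence 194, as stated.
- Noncentral t: the noncentrality is d√(n/2) = 0.5√44 = 3.317 on 174 df at 88 per group, and 0.5√48.5 = 3.482 on 192 df at 97 per group.
- Two-sided (critical value 1.974 at 88 per group, 1.972 at 97): a true favourable shift is detected with power 0.910 at 88 per group and 0.934 at 97. The chance of significance in the goal's direction is about 7×10⁻⁸ at 88 per group. The difference is found, but then judged against a goal of opposite sign.
- One-sided in the written direction (an assumption; critical value 1.654 at 88 per group): the power is 0.951 for an unfavourable shift and about 4×10⁻⁷ for an equal favourable one.

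**The case against.** The best defence is that the goals are not an isolated slip. They agree with the module aims, which seek to raise the perceived harm of sedentary life and, in the later stages, to lower its perceived benefit. They also agree with the introductory description of the scale, and the goals themselves do not say of what the benefit or harm is. On that reading they are coherent, and the fault is an undefined construct rather than two wrong signs.

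This explains how the conflict probably arose, and it stands as a reason to settle the construct explicitly. It does not rescue the goals. They concern scores, and those scores come from subscales that are named, interpreted and largely worded as benefit and harm of changing behaviour.

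Three smaller points also have force:

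- Item 8 is one item of a translated questionnaire, so it supports the argument without carrying it. The scoring sentences, the six utility items and harm items 2, 4, 6 and 12 are enough. The difficulty with item 10 may lie only in the English rendering.
- The power figures are for a comparison of two groups, while the goals are worded for the experimental group alone, and nothing says that these scores will be tested one-sided. The figures illustrate; the finding does not depend on them.
- The analysis would run identically whatever the goals say, and a careful author following Section 6.2.4 could still read the result correctly. Misreading is a risk, not a certainty.

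**Conclusion.** The concern holds. The utility and harm goals have the opposite sign to the scoring stated in Section 6.2.4 and repeated in Appendix 7. The extent is 2 of 14 goals, both SL-DBS subscales, with complete reversal. The conclusion assumes only that the subscales are scored as the protocol describes, with no unstated reversal.

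Two-sided testing loses no power; what is damaged is the reading of the result against its hypothesis. Power would be lost only under one-sided testing in the written direction, which the protocol does not state. The other 12 goals, data collection, scoring and sample size are unaffected. This should be corrected before results are known, but it does not threaten the trial as a whole.

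**What to change.** - Reverse the two goals and keep their within-group form: in the experimental group, the utility score (benefits of change) is expected to rise and the harm score (drawbacks of change) to fall.
- In the introductions to the scale (Section 6.2.4 and Appendix 7), state that benefit and harm refer to changing sedentary behaviour, as the scoring text and subscale names already do.
- In the module aims of Section 7, say explicitly when harm or benefit of sedentary life is meant, and do not present it as the quantity that the SL-DBS subscales score.
- Check item 10 against the Turkish form.

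If the sponsor did intend benefit and harm of sedentary life as the outcome, the goals could stand only with different scoring text, and the present items would not measure that construct.

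The cost is two reworded sentences and a few clarifying phrases. Nothing changes in data collection, scoring or sample size.

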- The place and time of the research; The research was planned to be carried out between September 2021 and September 2023 with university students studying in Istanbul Beykent University Vocational School health program.
- 3. The universe of the research; The universe of the research consists of Anesthesia Program (n=57), Operating Room Services Program (n=64), Oral and Dental Health Program (n=89), Medical Imaging Techniques (n=27) and First and Emergency Aid Program at Istanbul

Beykent University Vocational School. (n=53) university freshman students studying in departments with a high number of students and meeting the criteria for inclusion in the research constituted N=290. Students who meet the inclusion criteria and volunteer to participate will be included.

4. Sample; The sample of the study was calculated with the G-power (3.1.9.4) program, means: difference between two independent means analysis. When the effect size was 0.5, type error $\alpha = 0.05$, power 1- $\beta = 0.95$, the sample size was found to be 176 (experimental group 88, control group 88). Considering the sample loss that may occur due to various reasons, it was decided to include 194 (experimental group 97, control group 97) more than 10% of the sample. The groups will be randomly assigned to the experimental control groups through the SPSS program.

5. Inclusion, Exclusion, and Exclusion Criteria

5.1.Inclusion criteria for the study;

- First year students studying in Istanbul Beykent University Vocational School health program between September 2021 and September 2023,
- ➤ 18-25 years old,
- Being in the inactive (category 1) and minimally active (category 2) categories according to the International Physical Activity Evaluation Questionnaire,
- Not included in any physical activity program,
- Do not have any physical (orthopedic, chronic diseases, etc.) and mental problems diagnosed by a doctor,
- Accepting the measurement of body weight, height, body fat and muscle ratio and calculation of BMI before starting the research, at the 12th week and at the 6th month after its completion,
- > Agreeing to use pedometer (pedometer),
- > Having an iPhone, iPod touch and android based smart phone,
- ➢ Have an active internet connection on their phone,
- Students who voluntarily agree to participate in the research will be formed.

5.2. Exclusion and Exclusion Criteria;

➢ Willingness to leave the research.

6. Data Collection Tools and Format

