 - ✓ During deep inspiration, the distance between the thin bar parallel to the ground in contact with the head and the sole of the foot and the highest point of the head will be measured with an accuracy of 0.5 cm.
 - ✓ All measurements will be made in the same environment, at the same standard, at the same time and with the same tools.
- **6.2.6.4.Body mass index (BMI);** calculated by dividing the body weight by the square of the height.
 - ✓ According to the World Health Organization body mass index data, those below 18.5 kg/m2 are "thin", 18.5-24.99 range values are "normal", 25.0-29.9 kg/m2 are "slightly obese" and 30.0 kg/m2 m 2 or more is considered as "obese". When the study is completed, participants will be evaluated for body mass index (WHO, 2021).

Measurements;

All measurements will be made by the researchers. Measurements (T.C. Ministry of Health Patient Follow-up Guide; https://hsgm.saglik.gov.tr/depo/birimler/saglikli-bebek-hareketli-hayat-db/Haberler/Diyetsenler-Izlem-rehberi/Dietisyen_icin_hasta_izleme_rehberi.pdf, access date; 27.04.2022) was made using the source. In addition, the opinions of dietitians and physical therapists working in this field were taken.

6.2.7. Use of Pedometer (Smart Wristband) and Classification of Daily Step Count (Appendix 8)

A smart bracelet is a device used to monitor physical activity, showing how many steps are taken during the day. Step count measurement will be made with the Smart Bracelet. The smart bracelet has a Global Positioning System (GPS), that is, a global positioning system.

The smart bracelet is compatible with Android and iOS devices. The smart bracelet has a colorful, large and aesthetic display for blood pressure, pedometer, notification and message reading. It automatically records the number of steps and calculates the calories burned. The bracelet will vibrate slowly and give a warning when sitting or standing still for a long time. Charging time is one hour. On average, there is a need for a charge once a week. It has many features such as stopwatch, calendar, alarm clock.

Smart Wristband Usage:

Students will wear smart wristbands on their arms outside of sleep and shower. The smart bracelet will stay on the wrist for an average of 16 hours.

Number of Steps per Day: Tudor-Locke et al. divided the individuals into categories according to the number of steps. These;

Number of Steps Taken per Day	Category
less than 2500 steps	"basal activity"

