Educational videos to be used in the mobile software program will be prepared in the form of animation. Opinions and suggestions of sports trainers/trainers, physiotherapists and physicians/psychiatrists were received on the contents of the "Let's Move" Program prepared by the researchers.

8. **Intervention Plan of the Research**

Students whose activity scores are inactive and minimally active according to the results of the International Physical Activity Survey (IPAQ) will be included in the study.

Program with an online satisfaction survey.

The "Let's Move" Program will be shared with the control group.

9. Independent, Dependent and Control Variables of the Study

- The independent variable of the study; Mobile Software "Let's Move" Program Developed Based on Transtheoretical Model
- Dependent variables of the study; Number of Steps per Day, Physical activity MET score categories, Transtheoretic Model sedentary life Stages of Change, SL-SES score, SL-DBS benefit perception score averages, SL-DBS harm perception score averages, Physical activity walking, moderate, severe and total MET score averages, Body Mass Index categories, fat and muscle ratio values.
- Control variables of the study; age, gender, socio-economic level, people who do sports in the family, weather conditions, environmental conditions (areas where sports can be done), previous sports status
- Limitation of the research; The inability to include students who do not have an active internet connection was accepted as a limitation of the study.

10. Analysis and evaluation of research data

The analysis of the data will be carried out on the computer with the SPSS (Statistical Package for Social Sciences) 21 package program. In the statistical analysis of the data, descriptive analyzes will be given as percentage, mean and frequency. Chi-square will be used to evaluate the homogeneity of the Experimental and Control groups, and the t test or Mann Whitney U test will be used in the analysis of the data in the experimental and control groups. One Way Anova or Kruskal Wallis analysis of variance will be applied when comparing three or more groups. Statistical significance level will be accepted as p<0.05.

11. Ethical Permissions

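### The only BMI goal is the net share in a band bounded on both sides, an insensitive measure, although BMI in kg/m2 is already calculated

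*Protocol*

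**What the plan says.** - **Goal.** Under Objective/Reason, Project Goals, the only statement on BMI is "The proportion of those with normal Body Mass Index (18.5-24.99) in the experimental group will increase". The related body-composition goals have a direction: muscle ratio should rise, and "The body fat ratio of the experimental group will decrease".
- **Outcome.** The dependent variables in section 9 end with "Body Mass Index categories, fat and muscle ratio values". The same list gives MET and decisional balance results as averages. No goal or dependent variable uses mean BMI or change in BMI.
- **Calculation.** Section 6.2.6.4 has BMI "calculated by dividing the body weight by the square of the height", then sorts it into four classes: thin (below 18.5), normal (18.5-24.99), slightly obese (25.0-29.9) and obese (30.0 or more).
- **Timing.** Section 5.1 requires students to accept measurement of weight and height and calculation of BMI before the start, at week 12 and six months after completion.
- **Entry.** Section 5.1 selects on activity ("Being in the inactive (category 1) and minimally active (category 2) categories"), age, health, phone and consent. It sets no BMI limit.

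**The concern.** The normal band has a class below it and classes above it, and students from all of them can enter. If BMI falls in the experimental group, some students cross 25 downwards and join the band, while others cross 18.5 downwards and leave it. The goal counts only the balance. Students who start well inside the band and stay there contribute nothing, however much their BMI changes.

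A flat or lower normal share could therefore accompany a real fall in BMI, and the stated goal would not distinguish this from no change. The trial would judge its BMI goal on a weak summary of a number it already holds.

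**Working it through.** **1. The plan's own figure.** Section 4 sizes the trial for a difference between two means ("When the effect size was 0.5", alpha 0.05, power 0.95) and obtains 88 per group. With noncentrality 0.5 × √(88/2) = 3.32 and 174 degrees of freedom, power is 0.951 one-sided and 0.91 two-sided, so 88 reproduces as a one-sided calculation. It concerns a mean. The protocol gives no figure for BMI. I use 88 per arm and two-sided 0.05 below.

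**2. Assumed inputs (not in the protocol).** Baseline BMI is skewed: a gamma distribution starting at 15 kg/m2, with shape ((mean − 15)/SD)² and scale SD²/(mean − 15). BMI falls uniformly by 0.5 kg/m2 in the experimental arm and not at all in control.

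**3. Normal share.** With F the baseline distribution function and f the fall:
- share before = F(25) − F(18.5)
- enter = F(25 + f) − F(25)
- leave = F(18.5 + f) − F(18.5)
- share after = before + enter − leave

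Power for two proportions: h = 2|arcsin√p1 − arcsin√p2|, z = h√(88/2), power = Φ(z − 1.96) + Φ(−z − 1.96).

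| Mean, SD | Before | Enter | Leave | After | Power |
|---|---|---|---|---|---|
| 22.0, 3.3 | 70.6% | 2.8% | 5.4% | 68.0% | 7% |
| 22.5, 3.5 | 68.9% | 3.2% | 4.6% | 67.5% | 5% |
| 23.5, 3.8 | 64.1% | 3.9% | 3.2% | 64.8% | 5% |
| 25, 4 | 53.5% | 4.8% | 1.4% | 56.9% | 7% |

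The share falls in the first two rows and rises in the last two. In the first two its power is for a difference in the unintended direction.

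**4. Does this depend on the skew?** For a symmetric distribution the net change is zero when the mean equals the band's midpoint plus half the fall: (18.5 + 25)/2 + 0.25 = 22.0. With a normal distribution at mean 22.0, SD 3.3, the share is 67.4% before and after, with 3.7% moving each way. At mean 25, SD 4, it goes from 44.8% to 48.3%, with power 7.5%.

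**5. Larger fall.** With a 1.0 kg/m2 fall at mean 25, SD 4, where the share moves as intended, category power is still only 12 to 14%.

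**6. Mean BMI change.** Noncentrality = (0.5/SD of change) × √(88/2), two-sided t test:
- SD 0.8: 4.15, power about 98%
- SD 1.0: 3.32, power 91%
- SD 1.5: 2.21, power 59%

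For a 0.3 kg/m2 fall, power is 51 to 70% at change SD 1.0 to 0.8.

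**7. Where the gain comes from.** It depends on using the pre-test value. Post-test BMI alone with SD 3.5 gives noncentrality (0.5/3.5) × 6.63 = 0.95 and power of 16%. From change SD² = 2 × SD² × (1 − r), a baseline SD of 3.5 and change SDs of 0.8 to 1.5 imply pre-post correlations of 0.97 to 0.91. The category figures in step 3 compare follow-up shares without such adjustment. Adjustment would help them somewhat, but it cannot restore a net difference that has cancelled.

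**8. Size of an overweight subgroup.** In the first three rows, the fraction at 25 or more is 16.9%, 21.2% and 30.1%. Times 88, that is about 15, 19 and 26 to 27 students per arm.

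**The case against.** **No goal asks for a lower BMI.** More students in the normal band is a coherent aim, a student dropping below 18.5 rightly counts against it, and muscle gain with fat loss need not lower BMI. This stands. The protocol does not contradict itself here, and a reader should not infer that it set out to show a fall in BMI and chose a measure of something else.

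**Four categories are reported, not one share.** A full table would show thin rising and overweight falling even if normal is flat, and fat and muscle ratios are kept as values. This also stands. A reader might infer that the BMI outcome cannot detect any effect, or that a null result would say nothing about weight. Neither is supported. The offsetting arises when success is judged by the net normal share, which is how the goal is worded.

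**The direction depends on the assumptions.** If only students at 22 or above lose 0.5 kg/m2, nobody leaves at 18.5 and the share rises: 70.6% to 73.4%, 68.9% to 72.1% and 64.1% to 68.0% in the first three rows. So it cannot be said that the goal will point the wrong way. The insensitivity remains: the same arcsine formula gives power of only 7 to 8% for these differences.

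**A continuous summary is not precluded.** BMI is calculated as a number, and an analysis plan not shown here could use it. Section 9 nevertheless names the outcome, and names categories.

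**BMI is peripheral.** The Summary's list of effectiveness measures omits it. This limits the weight of the point but does not remove it.

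**Conclusion.** The point holds as one about sensitivity. The only BMI goal is a net share in a two-sided band, and the only BMI outcome is categorical, while the kg/m2 value is already planned at three times. For a uniform 0.5 kg/m2 fall and 88 per arm, power is about 5 to 7% for the normal share, against about 59 to 98% for baseline-adjusted mean BMI. Whether the share rises, stays flat or falls cannot be told from the protocol, because it gives no baseline BMI distribution.

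The figures rest on assumed baseline means of 22.0 to 25, SDs of 3.3 to 4, change SDs of 0.8 to 1.5 and a fall common to all students. The low power of the share persisted across every baseline tried, while its direction did not. This should be corrected, but it concerns one outcome among many and not the trial's main aim.

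**What to change.** - In section 9, list BMI in kg/m2 as the BMI outcome, compared between the experimental and control groups with adjustment for the pre-test value. Reword the BMI goal to match.
- Keep the four-category table as description. Report moves across 25 and across 18.5 separately, by group, and do not judge success by the net normal share.
- Any summary in students with BMI 25 or more at entry should be descriptive only. At assumed means of 22.0 to 23.5 it would hold about 15 to 27 students per arm, with two-sided power for a 0.5 kg/m2 fall of 26 to 62% (change SD 1.0 to 0.8).

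The cost is the wording of one goal and one outcome. Weight and height are already measured at all three times. One limit remains: an all-student mean does not separate desirable from undesirable falls, which is why the moves across 18.5 must be shown beside it.

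### The stated 95% power is a one-sided figure: at two-sided 0.05, 88 per group gives about 91%, and 95% would need 105 per group

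*Protocol*

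**What the plan says.** Item 4 (Sample) under Materials and Methods sizes the trial in G-power 3.1.9.4 with the procedure "means: difference between two independent means analysis". The inputs are a standardised effect ("When the effect size was 0.5"), alpha 0.05 and power 0.95. The result is that "the sample size was found to be 176 (experimental group 88, control group 88"). To allow for loss, "it was decided to include 194 (experimental group 97, control group 97) more than 10% of the sample". The paragraph does not say whether the calculation is one- or two-tailed.

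Section 10 (Analysis and evaluation of research data) says that "the t test or Mann Whitney U test will be used in the analysis of the data in the experimental and control groups". It adds chi-square for group homogeneity, and one-way ANOVA or Kruskal-Wallis for three or more groups. The only decision rule is "Statistical significance level will be accepted as p<0.05". No direction is given for any test.

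**The concern.** G-power asks the user to choose one or two tails for this procedure, and the answers differ substantially. The reported 88 per group looked too small for a two-sided test with these inputs.

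An undirected p<0.05 for a t or Mann-Whitney test is read as two-sided. If the sample size came from a one-tailed setting, the protocol claims a power that its own analysis rule does not deliver, and a null result would be presented as more informative than it is. If one-sided tests were really intended, nothing in the analysis section fixes that, and the threshold for significance could be settled after the data are seen.

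**Working it through.** **Inputs, all from item 4 (Sample):** d = 0.5, alpha = 0.05, power = 0.95, two independent means, equal groups, 88 per group, 97 per group after the loss allowance.

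**Method.** Exact power of the two-sample t test from the noncentral t distribution, with n per group:
- noncentrality δ = d·√(n/2), degrees of freedom 2n − 2;
- one-sided power = P(T > t at the 0.95 quantile);
- two-sided power = P(|T| > t at the 0.975 quantile).

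**Step 1: reproduce the protocol's figure.** At n = 88, δ = 0.5·√44 = 3.317 with 174 degrees of freedom. The one-sided critical value is 1.654 and power is 0.951. At n = 87 it is 0.9495, just short. So 88 is the smallest one-sided n, and 2 × 88 = 176 matches the protocol exactly. The normal approximation agrees: 2(1.645 + 1.645)²/0.25 = 86.6, rounded up to 87, one below the t-based answer.

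**Step 2: the same inputs, two-sided.** The normal approximation gives 2(1.960 + 1.645)²/0.25 = 104.0. The exact calculation gives power 0.948 at n = 104 and 0.950 at n = 105. The two-sided requirement is therefore 105 per group, 210 in total.

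**Step 3: power the design has at d = 0.5.**

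| Analysed per group | One-sided t | Two-sided t |
|---|---|---|
| 87 (97 less 10%: 97 × 0.9 = 87.3) | 0.949 | 0.907 |
| 88 | 0.951 | 0.910 |
| 97 (no loss) | 0.966 | 0.934 |
| 105 | 0.975 | 0.950 |

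**Step 4: Mann-Whitney.** Assuming an efficiency of 0.955 relative to the t test (normal data), the effective n is 0.955n. Two-sided power is 0.893 at 87 per group and 0.897 at 88.

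**Step 5: detectable difference.** With 88 per group, two-sided power reaches 0.95 at d = 0.5465, or about 0.55.

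**Loss allowance.** 176 × 1.1 = 193.6, rounded to 194, so 10% was added as described. Keeping 88 per group after a 10% loss would need 88/0.9 = 97.8, so 98. The gap is one student per group and changes two-sided power by 0.003.

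**The case against.** The strongest reply is that the arithmetic is not wrong. 88 is the correct one-sided answer, the protocol nowhere says two-sided, and its Project Goals are directional (steps and MET scores to rise, body fat to fall). On that view the fault is only undeclared sidedness, which declaring and justifying one-sided tests would also cure.

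Part of this stands. The two-sided reading rests on convention, not on a sentence in the protocol, and a declared one-sided plan would be consistent with 88. But the goals are never linked to one-sided testing, and chi-square and ANOVA in the same section are not directional tests. The goals are also an unsafe basis for choosing a direction. They expect the utility score to fall and the harm score to rise, whereas section 6.2.4 says that a high utility score makes change more likely and a high harm score makes it less likely.

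It is also fair to say that two-sided power stays above 90% for the t test, that type I error is unaffected, and that d = 0.5 is tied to no named outcome. These points limit the size of the problem without making the stated 95% right. The one-student gap in the loss allowance is trivial and the finding does not depend on it.

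**Conclusion.** The concern holds. The protocol's inputs give 88 per group only for a one-sided test that the protocol does not declare. Under the ordinary two-sided reading of p<0.05, power at d = 0.5 is 0.910 with 88 analysed per group. It lies between 0.907 and 0.934 across the range from 10% loss to no loss, so an unadjusted two-sided t test does not reach 0.95 at any point in that range. The type II error is about 9%, nearly double the stated 5%. This rests on the two-sided convention and on an unadjusted two-group comparison. The Mann-Whitney figures rest in addition on the assumed efficiency of 0.955.

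**What to change.** State in item 4 and in section 10 that tests are two-sided at 0.05. Restate the power along these lines: with 88 analysed per group, power is about 91% for a standardised difference of 0.5, and 95% for a difference of 0.55. This costs one reworded paragraph and a slightly less favourable power figure, with no extra students.

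There are two alternatives:
- **Keep 95% at d = 0.5.** Plan 105 per group before loss. That is 210 in total, or 210/0.9 = 233.3, so 234 with a 10% loss. It would take 234 of the 290 students in the source population (81%), against 194 (67%) now.
- **Keep 88 as a one-sided calculation.** Declare and justify one-sided tests in both places, and first resolve the direction of the decisional balance scores.

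A baseline-adjusted comparison would recover some or all of the power, but section 10 plans none and the protocol gives no baseline to follow-up correlation r. Replacing d by d/√(1 − r²), two-sided power at 88 per group would be 0.920 for r = 0.2, 0.933 for r = 0.3, 0.949 for r = 0.4 and 0.968 for r = 0.5. If this route is taken, the assumed correlation should be stated.
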